6.6.2. Restarting Study Drug after Interruption

In certain situations, the investigator may need to temporarily interrupt study drug. Every effort should be made by the investigator to maintain participants on study drug and to restart study drug after any temporary interruption, as soon as it is safe to do so. Distribution of study drug at the correct dose will be per IWRS instructions.

If study drug interruption is	then
1 or 2 consecutive doses	Participant restarts study drug at last administered dose, per escalation schedule. If the participant has reached maintenance dose level, the study drug dose level will restart at the same prior achieved maintenance dose level.
3 or more consecutive doses	Participant restarts study drug (at 5 mg, managed by IWRS) and repeats dose escalation scheme until maintenance dose is reached. If maintenance dose has previously been established, the dose escalation cannot not exceed the prior achieved maintenance dose level.
Due to an AE	The event is to be documented and followed according to the procedures in Section 8.3.
Due to intolerable persistent GI AE	Participants should be treated as suggested in Section 6.5.

Abbreviations: AE = adverse event; GI = gastrointestinal; IWRS = interactive web response service.

Investigators should inform the sponsor that study drug has been temporarily interrupted.

Participants are not required to re-escalate to the prior maintenance dose level if a tolerability issue recurs during dose re-escalation.

If this attempted dose re-escalation to the prior maintenance dose level is not tolerated, the dose should be reduced to the next lower 5 mg incremental dose that was tolerated (for example, 5 mg or 10 mg). The participant will remain at that dose level for the duration of the study. During re-escalation after a temporary dose interruption, participants should be followed every 4 weeks until either a new lower maintenance dose level or prior maintenance dose level is reached.

For participants receiving 5 mg maintenance dose, no dose de-escalation is permitted. Only dose interruption is permitted to manage tolerability issues (Section 6.6.2). This can be performed through IWRS.

In the event that a participant has a temporary interruption that requires extending the escalation beyond Visit 8, unscheduled visits are allowed in the IWRS to facilitate a 4-week dispensing schedule to complete the escalation.

If an unscheduled visit occurs in the same week or date of a regular scheduled visit per the SoA, the site should complete all procedures included for the regular scheduled visit. Unscheduled

visits either in the clinic or by telephone may be conducted to provide support and guidance to participants as needed.

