At Visit 2, prior to randomization, the participant needs to complete the 6MWT. Visit 2 may need to be conducted over 2 in-clinic visits (considered Visit 2a and Visit 2b) if a repeat 6MWT is necessary to assess participant eligibility. If the participant is required to return to repeat the 6MWT, the remaining procedures should be conducted at the second in-clinic visit for randomization (Visit 2b), more than 10 days from Visit 2a. See Section 10.10.1 for details on when a participant must return for a second Visit 2 6MWT.

Participants will be randomized and receive blinded study drug at the end of Visit 2 after all screening procedures are completed. The participant must not receive study drug until all eligibility criteria, including the 6MWT, are met.

Treatment

Starting from randomization, the participant receives study drug and procedures are conducted as described in the SoA (Section 1.3). Every effort should be made by the investigator to maintain participants on study drug.

Study drug dose will be escalated as illustrated in the study schema (Section 1.2). Dose escalation will continue until the participant reaches the maintenance dose of either 5 mg, 10 mg, or 15 mg. Participants who do not tolerate the first dose escalation (that is, from 2.5 mg to 5 mg [or placebo equivalent]) will need to discontinue from study drug.

Participants begin treatment with either tirzepatide or placebo starting at 2.5 mg given as a subcutaneous (SC) injection every week (QW). The dose level is increased by 2.5 mg increments approximately every 4 weeks for the first 20 weeks according to the participant's tolerability, reaching a MTD up to 15 mg. Once a MTD has been achieved, participants will continue at this MTD until study end, treatment discontinuation, or study discontinuation. Dose modifications will be permitted during the study under the circumstances specified in Section 6.6.

During the study treatment period, if an unscheduled visit or telephone visit is deemed necessary to support participant compliance, this is allowable at the discretion of the investigator site personnel. Optional telephone visits can be performed approximately 2 weeks after starting study drug and after each dose increase.

Participants will continue into the extended maintenance period with the same treatment assignment starting with Visit 13. Extended visits (EV) continue until criteria for study discontinuation is met or study ends (see Study Closeout and Final Visit below).

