4.3. Justification for Dose

Tirzepatide doses of up to 15 mg administered SC QW will be evaluated in this study.

Participants may be treated with lower maintenance doses of 5 mg or 10 mg if they do not achieve full dose escalation to 15 mg and/or do not tolerate 15 mg.

These doses and associated escalation schemes were selected based on assessment of safety, efficacy (glycemic and weight loss benefit), and GI tolerability data followed by exposure response modeling of data in participants with T2DM in Phase 1 and Phase 2 studies. Dosing algorithms starting at a low dose of 2.5 mg accompanied by dose escalation of 2.5 mg increments every 4 weeks should permit time for development of tolerance to GI events and are predicted to minimize GI tolerability concerns.

The dose selection of tirzepatide is based on the findings of the Phase 2 study results. Tirzepatide doses of 5 mg, 10 mg, and 15 mg QW have been tested and compared with dulaglutide 1.5 mg QW or placebo in a Phase 2 study (Frias et al. 2018). While all 3 doses of tirzepatide significantly improved the glycemic control versus dulaglutide, the largest difference was observed in the 15-mg tirzepatide treatment group. Moreover, the reduction in body weight with tirzepatide was also dose-dependent and greatest in the 15 mg QW treatment group.

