6.6. Dose Modification

Interventions to optimize study drug tolerance and adherence may be employed throughout the study and include, but are not limited to, brief temporary interruptions and use of additional medications to manage symptoms.

Dose modifications, including temporary interruption and de-escalation may occur to manage issues with tolerability. It is preferred to attempt a temporary dose interruption (at any time) (Section 6.6.1) to manage tolerability issues. After a temporary dose interruption, participants may resume study drug at the same dose, re-escalate to the prior dose level (if re-escalation is desired or required), or resume at a lower MTD dose level, as tolerated. Guidance for resuming study drug after a temporary dose interruption should be followed (Section 6.6.2).

Unwarranted excessive weight reduction: Dose interruption is preferred over de-escalation for slowing unwarranted excessive weight loss; however, the method used is at the investigator's discretion. After the dose escalation period and at the investigator's discretion, when excessive weight reduction is not warranted due to safety concerns, the investigator may choose to adjust the study drug dose without first attempting a temporary dose interruption. The participant's study drug dose will be permanently reduced to 5 mg, in a blinded fashion for the remainder of the study and the dose cannot be re-escalated. A dose adjustment for unwarranted excessive weight reduction is completed through the IWRS. Participants on 5 mg will have blinded study drug temporarily interrupted (Section 6.6.1).

Dose reductions for unwarranted excessive weight loss may occur at scheduled and unscheduled visits.

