6.6.1. Temporary Interruption

Temporary study drug interruption should be utilized to manage tolerability issues. After randomization, the investigator may interrupt study drug, for example, due to an AE (such as nausea vomiting, excessive unwarranted weight loss or a clinically significant laboratory value). Guidance for resuming study drug after a temporary dose interruption should be followed (Section 6.6.2). If study drug interruption is due to an AE, the event is to be followed and documented.

For cases where increased ALT, AST, or ALP occurs, study drug may be interrupted (Section 6.6.2), and close hepatic monitoring must be initiated (Section 8.2.5.1). The interruption of study drug is not equivalent to discontinuation from study treatment. Any interruption of study drug does not affect the study visit structure/schedule per the SoA (Section 1.3). Even if study drug is interrupted, study procedures should continue during the dose interruption. Every effort should be made by the investigator to maintain participants in the study and to restart study drug promptly after any interruption, as soon as it is safe to do so (see Section 6.6.2. for restarting study drug). Dose interruptions are managed through the IWRS. The data related to interruption of study drug will be documented in source documents and entered on the eCRF, however participant noncompliance should not be recorded as interruption of study drug on the eCRF.

Participants who have a temporary interruption of the study drug will continue participating in the trial according to the protocol to collect all planned efficacy and safety measurements (Section 1.3).

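### The 5 mg restart after three or more interrupted doses has no exception for participants still in the 2.5 mg step, so some restart at a dose they have never taken

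*Protocol*

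**What the plan says.** The restart table in Protocol Section 6.6.2 sets the dose by the length of the interruption.

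- **One or two consecutive doses:** "Participant restarts study drug at last administered dose, per escalation schedule".
- **Three or more consecutive doses:** "Participant restarts study drug (at 5 mg, managed by IWRS) and repeats dose escalation scheme until maintenance dose is reached". The only qualifier is "If maintenance dose has previously been established, the dose escalation cannot not exceed the prior achieved maintenance dose level".

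Section 6.6 describes resumption in general terms: "participants may resume study drug at the same dose, re-escalate to the prior dose level", or resume at a lower tolerated level. It then refers the reader to Section 6.6.2 for the actual guidance.

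Section 6.1 schedules 2.5 mg for Weeks 0 to 3 and 5 mg for Weeks 4 to 7. Section 4.3 gives the reason for small steps from a low starting dose: increments "every 4 weeks should permit time for development of tolerance to GI events".

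Interruption is possible at any time after randomization. Section 6.6.1 states that "the investigator may interrupt study drug, for example, due to an AE (such as nausea vomiting" is among the reasons. On the step from 2.5 mg to 5 mg, Section 4.1 is strict: "Participants who do not tolerate the first dose escalation" have to come off study drug.

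**The concern.** The row for three or more doses suits a participant who was at 7.5 mg or above, or who has at least taken 5 mg: it steps the dose down, or repeats a known one, after time off drug. It does not suit a participant who has not finished the 2.5 mg step. There it raises the dose, after both a short exposure and a gap.

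The maintenance-dose cap gives no protection, because a participant at 2.5 mg has no maintenance dose. The result is also out of order: with the same dose history, the longer gap leads to the higher restart dose.

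What is at stake is tolerability and retention on drug. Nausea and vomiting are named reasons to interrupt, so the affected group can include people who have already had gastrointestinal symptoms at 2.5 mg. They would meet 5 mg with less time at 2.5 mg than Section 4.3 intends, and failing the first escalation leads to stopping study drug.

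**Working it through.** The plan gives no figure on this point to reproduce. The check applies the written rules to each possible early dose history.

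**Inputs**

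- 2.5 mg is given weekly at Weeks 0, 1, 2 and 3, so the step has four doses (Sections 4.1 and 6.1).
- Each later step is 2.5 mg higher and lasts four weeks (Sections 4.1 and 6.1).
- One or two interrupted doses: restart at the last dose given. Three or more: restart at 5 mg (Section 6.6.2).

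**Restart week**

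Restart week = week of last dose + number of interrupted doses + 1. For example, with the last dose at Week 0 and three interrupted doses, 0 + 3 + 1 = Week 4.

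| Last dose | 2.5 mg doses taken | Restart after 2 interrupted doses | Restart after 3 interrupted doses | 5 mg first taken at restart, with the step unfinished? |
|---|---|---|---|---|
| Week 0 | 1 of 4 | Week 3, 2.5 mg | Week 4, 5 mg | Yes |
| Week 1 | 2 of 4 | Week 4, 2.5 mg | Week 5, 5 mg | Yes |
| Week 2 | 3 of 4 | Week 5, 2.5 mg | Week 6, 5 mg | Yes |
| Week 3 | 4 of 4 | Week 6, 2.5 mg | Week 7, 5 mg | No: step complete, 5 mg is the planned next dose |

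From the fifth dose onward 5 mg has already been taken, so the problem does not arise. Three dose histories are affected. In each, the calendar schedule also shows 5 mg at the restart week in the table, so the rule does not run ahead of the calendar. It runs ahead of the participant's exposure.

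**Does another section supply a lower restart dose?**

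- Section 6.6 lists the same dose, the prior level or a lower level. A first-ever higher dose is none of these, but the section defers to Section 6.6.2.
- The row for intolerable persistent gastrointestinal events sends the reader to Section 6.5, which sends the reader back to Section 6.6.2 after an interruption.
- The requirement to restart once it is safe (Sections 6.6.1 and 6.6.2) governs when to restart, not the dose.
- The step-down rule in Section 6.6.2 gives 5 mg or 10 mg as examples, and a 5 mg maintenance dose may not be reduced.

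None of these leads to 2.5 mg.

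**Time to 15 mg, exactly three interrupted doses**

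- Current rule: from 5 mg there are (15 − 5) / 2.5 = 4 steps, and 4 × 4 = 16 weeks. Restart at Week 4, 5 or 6 gives 15 mg at Week 20, 21 or 22.
- With a full 4-week step at 2.5 mg first: 16 + 4 = 20 weeks, so Week 24, 25 or 26.
- Time left before the Week 52 assessment in the latest case: 52 − 26 = 26 weeks.

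**The case against.** The strongest objection is that the row says the restart is managed by the IWRS, whose specification is not in the documents. Sites dispense what the system assigns, so no dosing error is demonstrated. That stands as a limit on what can be known. It does not rescue the text, because the written rule the system would implement says 5 mg.

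Second, no rule requires four 2.5 mg doses before 5 mg. Section 6.1 assigns dose by calendar interval, and Section 4.3 is rationale, not a minimum count. This is correct, and 5 mg is the calendar dose at restart. But weeks off drug are not weeks of exposure, and the rationale concerns tolerance built up during dosing.

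Third, the row for one or two doses adds that the restart follows the escalation schedule. On one reading, a participant could then reach 5 mg after fewer than four 2.5 mg doses. The wording is ambiguous, and the change proposed here would not settle it. The restart dose in that row is still the last one given, 2.5 mg.

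Fourth, discontinuation is not immediate. Interruption is the preferred response, gastrointestinal management is available, the sponsor must be contacted before permanent discontinuation, and a participant off drug stays in the study. These safeguards soften the consequence, but none of them changes the restart dose.

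Finally, the group is small. The interruption must last at least three doses and begin within the first three weekly doses, and Section 6.6.1 does not count noncompliance as an interruption. This limits the weight of the point but does not remove it.

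**Conclusion.** The concern holds. As written, Section 6.6.2 restarts at 5 mg a participant who has taken only one to three 2.5 mg doses, and no other section provides an exception. This is a stated rule that gives a poor result in a narrow early group, not a missing detail.

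Its size in participants cannot be given, because the documents state no expected frequency. It affects three dose histories, for recorded interruptions only. The conclusion rests on the written protocol and assumes the IWRS follows it. The documents do not state enrolment status, and a change would help only participants who have yet to start or complete the 2.5 mg step. No sample-size, power or alpha figure is affected. The change is worth making mainly because it costs little.

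**What to change.** Add to the row for three or more doses: a participant who has not completed the four weekly 2.5 mg doses and has not yet taken 5 mg restarts at 2.5 mg and completes a 4-week step at that dose before escalating. Confirm that the IWRS logic matches the revised row.

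The cost is one sentence and one system check. The downside is a delay in escalation of about four weeks for the few participants affected, as shown in the working. Section 6.6.2 already provides for escalation that runs past Visit 8 (Week 24): "unscheduled visits are allowed in the IWRS to facilitate a 4-week dispensing schedule to complete the escalation".

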6.7. Intervention after the End of the Study

Tirzepatide will not be made available to participants after conclusion of the study. Due to the double-blind study drug assignment, it is not known if a participant received active study drug or placebo. Participants will not be unblinded until study end and the final analyses are complete.

7. Discontinuation of Study Intervention and Participant Discontinuation/Withdrawal

7.1. Discontinuation of Study Intervention

7.1.1. Permanent Discontinuation from Study Drug

Before permanently discontinuing study drug, attempts to maintain the participant should be documented (see Dose Modification, Section 6.6 and Temporary Dose Interruption, Section 6.6.1). Contact the sponsor before study treatment discontinuation occurs to discuss potential options to maintain the participant on study drug until final study ends. It is the goal for participants to remain on study drug treatment until study ends.

Permanent discontinuation of study drug will not automatically lead to discontinuation from the study. If study drug is permanently discontinued, the participant will remain in the study and attend all scheduled visits to be evaluated for safety and efficacy as described in the SoA.

Possible reasons leading to permanent discontinuation of study drug:

• Participant decision

 The participant or the participant's designee (for example, legal guardian) requests to discontinue study drug

• Investigator Decision

o The investigator decides that the participant should be discontinued from study drug

• Discontinuation due to a hepatic event or liver test abnormality

Please refer to Section 8.2.5.1 for liver chemistry stopping criteria and Section 8.2.5.4 for study drug interruption or discontinuation due to an hepatic event. Participants who experience a hepatic event or liver test abnormality should have additional hepatic safety data collected via CRF (see Section 8.2.5.1 for details). Resumption of the study drug can be considered only in consultation with the Lilly-designated medical monitor and only if the liver test results return to baseline and if a self-limited non-drug etiology is identified.

- In addition, participants will be permanently discontinued from the study drug in the following circumstances:
 - o acute or chronic pancreatitis (see Section 10.5.1.2)
 - o if a participant is diagnosed with thyroid C-cell hyperplasia, MEN-2, or MTC, or pancreatic cancer after randomization
 - o if any other TEAE, SAE, or clinically significant laboratory value for which the investigator believes that permanent study drug discontinuation is the appropriate measure to be taken
 - o if a participant is diagnosed with T1DM
 - o if a female participant becomes pregnant
 - o if an investigator, site personnel performing assessments, or participant is unblinded

o if the investigator, after consultation with the sponsor-designated medical resource, determines that a clinically significant systemic hypersensitivity reaction has occurred. A clinically significant systemic hypersensitivity reaction is one that occurs after administration of the study drug (for example, drug-related symptomatic bronchospasm, allergy-related edema/angioedema, or hypotension) and requires parenteral medication, does not respond to symptomatic medication, results in clinical sequelae, or is an anaphylactic reaction.

- o if the participant undergoes any bariatric surgery during the study
- o if the participant begins treatment with a GLP-1RA during the study,
- o in the opinion of the investigator, the participant should permanently discontinue the study intervention for safety reasons.

7.2. Participant Discontinuation/Withdrawal from the Study

In order to minimize the amount of missing data and to enable assessment of study objectives as planned in the study protocol, every attempt will be made to keep participants in the study, irrespective of the following:

- compliance to study drug
- adherence to visit schedule
- missing assessments
- study drug discontinuation due to AE (Section 7)
- development of comorbidities, and
- development of clinical outcomes.

The circumstances listed above are *not* valid reasons for participant discontinuation from the study.

Participant will be discontinued from study in the following circumstances:

- enrollment in any other clinical study involving a study drug or enrollment in any other type of medical research judged not to be scientifically or medically compatible with this study
- participation in the study needs to be stopped for medical, safety, regulatory, or other reasons consistent with applicable laws, regulations, and GCP, and
- if the participant becomes pregnant.

A participant may discontinue from the study:

- at any time at his/her own request
- at the request of his/her designee (for example, legal guardian)
- at the discretion of the investigator for safety, behavioral, compliance, or administrative reasons
- if enrolled in any other clinical study involving an investigational product, or enrolled in any other type of medical research judged not to be scientifically or medically compatible with this study, or

• if the participant, for any reason, requires treatment with a therapeutic agent that is prohibited by the protocol and has been demonstrated to be effective for treatment of the study indication. In this case, discontinuation from the study occurs prior to introduction of the new agent.

Study discontinuation is expected to be rare and participants should be provided with options for alternative follow-up methods and/or end of study vital status/endpoint ascertainment.

If the participant is unwilling or unable to return for all scheduled follow-up visits in person, the site will attempt to collect as much follow-up information as possible via telephone or other virtual methods of direct patient contact with the patient. Sites are expected to conduct these alternative visit methods according to the visit interval outlined in the Schedule of Activities.

An ET visit should be conducted, as shown in the SoA. If the participant refuses to have an ET visit in the clinic, efforts should be made to collect data via telephone. See the SoA for data to be collected at the time of ET visit. If the participant has not already discontinued the study intervention, the participant will be permanently discontinued from the study intervention at the time of the decision to discontinue the study.

If the participant withdraws consent for disclosure of future information, the sponsor may retain and continue to use any data collected before such a withdrawal of consent. If a participant withdraws from the study, he/she may request destruction of any samples taken and not tested, and the investigator must document this in the site study records.

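### Protocol 7.2 permits study exit before a prohibited effective agent is started, 7.1.1 keeps a GLP-1RA starter in the study, and no precedence is stated; used before Week 52, the exit puts Week 52 data at risk

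*Protocol*

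**What the plan says.** Protocol 7.2 has three lists. The first gives circumstances that are not valid reasons for leaving the study, including "compliance to study drug". The second gives mandatory exits. The third is optional and opens with "A participant may discontinue from the study". Its final bullet covers a participant who needs an agent that the protocol prohibits and that has been shown to work in the study indication, and it fixes the timing: "In this case, discontinuation from the study occurs prior to introduction of the new agent". The same optional list allows exit "at the discretion of the investigator for safety, behavioral, compliance, or administrative reasons".

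Section 7.1.1 lists events that end study drug permanently. One is "if the participant begins treatment with a GLP-1RA during the study". The consequence is stated in the same section: "If study drug is permanently discontinued, the participant will remain in the study and attend all scheduled visits". Section 7.1.1 also tells the site to contact the sponsor before study treatment is discontinued.

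On retention, 7.2 says "Study discontinuation is expected to be rare", asks that alternative follow-up or endpoint ascertainment be offered, and adds that for a participant who cannot or will not attend in person "the site will attempt to collect as much follow-up information as possible via telephone or other virtual methods".

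Protocol 9.4.2 and 9.4.3 and SAP 3.13.1 and 3.13.2 apply the treatment-policy strategy to the Week 52 endpoints (for hsCRP, to all intercurrent events except death).

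**The concern.** A GLP-1RA can meet both conditions of the 7.2 bullet on the protocol's own text. Section 6.5 prohibits all GLP-1 RAs, and 2.2 cites a placebo-controlled HFpEF trial in which semaglutide improved KCCQ-CSS and 6MWD. One participant can therefore fall under the 7.2 exit and the 7.1.1 retention rule. Section 7.2 acts first, at the point of need, so a site that uses it removes the participant before 7.1.1 can apply.

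Under treatment policy, Week 52 values after a GLP-1RA start are part of what the trial sets out to estimate. An early exit puts them at risk. It also removes a possible donor for the retrieved-dropout imputation, which draws on same-arm participants observed at Week 52 after stopping study drug.

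Separately, 7.2 rules out compliance with study drug as a reason for exit and then permits investigator-discretion exit for compliance. No size is claimed for that wording conflict.

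**Working it through.** **Which rule applies.**

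| | 7.1.1 | 7.2, last optional bullet |
|---|---|---|
| Trigger | GLP-1RA is begun | Prohibited, effective agent is needed |
| Force | Mandatory stop of study drug | Optional exit from study |
| Week 52 visit | Continues | Not scheduled; alternative follow-up to be offered |

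Starting a prohibited agent is in neither the list of invalid reasons nor the list of mandatory exits in 7.2. Sections 6.5, 7.1.1 and 7.2 and the SAP state no precedence.

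**What happens to the Week 52 values after a 7.2 exit.**

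- *6MWD.* Protocol 8.1.2.1 requires an indoor course of at least 30 m and describes no remote version. The value is at risk unless the participant comes back in person. The same section requests a late test within 30 days of a missed Visit 12.
- *Weight and hsCRP.* These need a calibrated scale (8.2.1) and a central-laboratory sample (10.2), so they are at risk in the same way.
- *KCCQ-CSS.* Participants enter it themselves on a device (10.1.6), and 8.1.1.1 has the same 30-day request. It can be recovered in person or remotely.
- *Early-termination tests.* KCCQ and 6MWT are required at that visit, but before the new agent is started. The SAP does not use them as Week 52 values for these endpoints. It has such a rule only for the MRI substudy (Appendix 3).
- *If missing.* SAP 3.13.1.3 imputes from same-arm retrieved dropouts, or by reference to placebo if these are too few. Those donors stopped study drug for any reason and need not resemble GLP-1RA users.

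**The plan's own figure.** Protocol 9.2 gives 350 per arm, a 5-point KCCQ-CSS difference, SD 19, two-sided alpha 0.01 and roughly 80% power. Power = Φ(5 / (19·√(2/n)) − 2.576). With n = 350 this is 81.7%; with n = 350 × 3/π = 334.2, for the efficiency of the Wilcoxon test, it is 79.6%. The stated figure reproduces.

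**Illustrative ceiling.** The documents give no exit rate. Assume a share e of an arm, 0.5% to 5%, leaves by this route before Week 52: 350 × 0.005 = 1.75 to 350 × 0.05 = 17.5, or about 2 to 18 participants. Suppose each would have gained the full effect cited in 2.2 (7.8 points, 20.3 m) and the imputed value carries none of it. The fall in that arm's mean is e × effect:

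- 6MWD: 0.005 × 20.3 = 0.10 m to 0.05 × 20.3 = 1.0 m.
- KCCQ-CSS, if not collected: 0.005 × 7.8 = 0.04 to 0.05 × 7.8 = 0.39 points. Against the planned 10 − 5 = 5 points that is 0.8% to 7.8%; 0.39/19 is about 0.02 SD.

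Net shift in tirzepatide minus placebo = effect × (e placebo − e tirzepatide):

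| Exit, placebo | Exit, tirzepatide | 6MWD (m) | KCCQ-CSS (points) |
|---|---|---|---|
| 5% | 0 | +1.0 | +0.39 |
| 5% | 2.5% | +0.51 | +0.20 |
| 5% | 5% | 0 | 0 |
| 2.5% | 5% | −0.51 | −0.20 |
| 0 | 5% | −1.0 | −0.39 |

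**Power.** If those who exit add no information, KCCQ-CSS power falls from 79.6% to 79.1% with 1% leaving each arm and to 77.0% with 5% leaving each arm. With 5% leaving placebo only it is 78.3%.

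Both tests are rank-based, so mean shifts give only a rough scale.

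**The case against.** The strongest reply is that there is no conflict to resolve. Section 7.1.1 is specific and mandatory, while the 7.2 bullet is general and optional and sits in a section whose stated aim is to keep participants in the study. A site can follow 7.1.1 alone without breaching 7.2. Sponsor contact before study drug stops, and the invitation in 6.5 to ask the sponsor about concomitant therapy, limit variation between sites. The trigger is also narrow: 2.2 supports efficacy for semaglutide only, and 4.2 says no therapy is approved in this population. Many GLP-1RA starts might not qualify.

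All of this stands, and it limits the point to an unresolved overlap on an optional path. It does not remove the overlap. An optional exit that takes effect before the retention rule can apply still invites avoidable missing data, and the documents do not tell a site, or the sponsor when contacted, which rule to follow.

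A reader might infer three stronger things. The documents do not support them:

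- *That 7.2 requires exit, or contradicts 7.1.1.* The bullet is in the optional list.
- *That the Week 52 6MWD is necessarily missing after exit.* Section 7.2 asks for alternative follow-up and endpoint ascertainment, reserves telephone contact for those who cannot or will not attend, and so does not rule out an in-person test.
- *That the bias favours tirzepatide.* That needs more such exits on placebo. Exits mainly on tirzepatide would do the reverse, and same-arm imputation from participants kept under 7.1.1 could offset either.

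**Conclusion.** The point holds as a correctable wording gap. A stated rule permits exits that work against the treatment-policy estimand, and its relation to the retention rule in 7.1.1 is left open. Week 52 6MWD, weight, hsCRP and KCCQ-CSS are at risk, KCCQ-CSS least because it can be collected remotely. CV death and HF events are less affected where follow-up continues; otherwise the participant is censored at the end of follow-up.

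The number affected is unknown and should be small. Under the assumed 0.5% to 5% exit in one arm only, the ceiling is 0.1 to 1.0 m and 0.04 to 0.39 points, with the sign depending on the arm; equal exits give zero. The ceiling credits every exiter with a full 52-week effect whenever the agent was started, so it probably overstates the shift. Nothing here shows that a trial conclusion would change. The case for acting is that the loss is avoidable and the correction is cheap.

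**What to change.** Replace the last optional bullet in 7.2 with a cross-reference to 7.1.1. State that starting a prohibited agent shown effective for the indication stops study drug only, and that Week 52 KCCQ, 6MWT, weight and hsCRP and follow-up for HF events continue. Delete compliance from the investigator-discretion bullet so that it agrees with the list of invalid reasons in the same section.

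The cost is a minor protocol amendment, with the IRB/IEC approval that 10.1.1 requires (and health authority approval if it is classed as substantial), and a site memo. No procedure is added, because the visits are already in the schedule. The participant's right to withdraw at any time is unchanged, so exits at the participant's own request will still occur; the edit removes only the protocol's own prompt to leave.
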